6.2.4. Persistence Assessment Oral PrEP

6.2.4.1. The proportion of participants who initiated oral PrEP who remained on oral PrEP at months 3 and 12 measured by the self-report assessment and validated with claims data period.

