6.2.3. Persistence Assessment CAB-LA

6.2.3.1. The proportion of participants who received at least one PrEP injection who remained on injectable PrEP or oral bridging at months 3 and 11 measured by the self-report assessment and validated with claims data.

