6.6. PrEP Discontinuation

6.6.1. Participants will be deemed as having discontinued PrEP if they miss more than 3 consecutive months for PrEP.

6.6.2. Participants will be called, texted and emailed for three consecutive months before considered them as discontinued.

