6.13. Interventions: PrEP Initiation and Digital Health Companion Program

6.13.1. Participants will be enrolled in the CAB-LA and Oral PrEP cohorts. Participants in the CAB-LA cohort will receive their first dose of the PrEP injection at month 0. Injections will also be administered in months 1, 3, 5, 7, 9, and 11. Participants in the Oral PrEP cohort will have their prescription filled at month 0, 3, 6, 9, and 12. The schedule of dosing is presented in Figure 6a.

6.13.2. Participants in both cohorts will complete education modules and health literacy evaluations in the TheraPay App in months 2, 4, 6, 8, and 10 as presented in Figure 6a. Education Modules include PrEP Medicines (month 2), Protecting Yourself from HIV, STIs, and other infections (month 4), Building a Support System for HIV Prevention Month 6: Being an Active Participant in Your Own Care (month 8), and Overcoming Stigma and Becoming a Health Advocate (month 10).

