To assess the co-primary endpoint of persistence at 3 months and end of study, the proportion of participants reporting continued receipt of injections in the CAB-LA cohort and the proportion of patients reporting continued use of PrEP by mouth in the oral PrEP cohort on the persistence assessment will be compared using chi square tests or Fisher's exact tests. Self-reported persistence will be validated by the medication possession ratio (MPR). MPR is defined as the number of days of medication dispensed during the study period divided by the number of days that the person should have received therapy. The percent of CAB-LA participants with MPRs ≥ 1.0 will be compared to the percent of oral PrEP participants with MPRs ≥ 1.0 using chi square tests or Fisher's exact tests. To assess the co-primary endpoint of adherence, chi square tests or Fisher's

exact tests will be used to compare the percent of CAB-LA participants who reported missing one or more injections during the study period to the percent of oral PrEP participants who reported three or more missed days of oral PrEP. The percent of CAB-LA participants who received any injections seven or more days later than their scheduled injection or oral PrEP participants who had a gap of >90 days between the end of the days of supply of a dispensing and the start date of the next fill will be compared.

Sample Size

Assuming adherence proportions of .90 and .65 and sample sizes of 70 and 35 in the CAB-LA and oral PrEP arms respectively, the 95% confidence interval for the difference between the CAB-LA proportion and the oral PrEP proportion is .0771 to .4229.

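### As defined, the medication possession ratio does not test self-reported persistence at month 3: read at that point it is about 1.0 for every oral initiator, including one who never returns

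*Combined protocol and SAP*

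**What the plan says.** Section 6.2.4 defines oral persistence as the proportion of initiators who "remained on oral PrEP at months 3 and 12 measured by the self-report assessment and validated with claims data period". Section 6.2.3 defines CAB-LA persistence, among those with at least one injection, as the proportion who "remained on injectable PrEP or oral bridging at months 3 and 11 measured by the self-report assessment and validated with claims data".

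The supply calendar is in Section 6.13. For oral PrEP: "Participants in the Oral PrEP cohort will have their prescription filled at month 0, 3, 6, 9, and 12". For CAB-LA, the first injection is at month 0, and "Injections will also be administered in months 1, 3, 5, 7, 9, and 11".

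Section 7 makes persistence at month 3 and at end of study a co-primary endpoint. It compares the self-reported proportions by chi-square or Fisher's exact test. MPR is the validator, computed by taking "the number of days of medication dispensed during the study period divided by the number of days that the person should have received therapy", and the shares of each arm at 1.0 or above are compared. The Study Outcomes Table also lists the EHR as a data source, but gives no rule for using it.

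Section 6.6.1 adds a discontinuation rule: "Participants will be deemed as having discontinued PrEP if they miss more than 3 consecutive months for PrEP".

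The plan does not state the days' supply per fill, an MPR window for month 3, or whether the refill due at month 3 counts toward month-3 persistence.

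**The concern.** The first oral refill falls due at the early reading itself. Up to that point the oral dispensing record consists of the month-0 fill alone, whatever the participant has done since. CAB-LA has one scheduled dose, at month 1, before the same reading, so one kind of early lapse can show in that arm's records.

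MPR is the only validator for which the plan gives a rule. If it cannot contradict an oral participant who answers yes at month 3, agreement between self-report and records means little in that arm, and the two arms are checked with different sensitivity. A reader of the results could take the validation as support for early oral persistence when it carries almost no information.

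A second gap sits beside this. The discontinuation rule needs more than three missed months, yet the endpoint counts stops at month 3. The plan does not say whether the rule plays any part in scoring.

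**Working it through.** **The plan's own figure.** The only interval given is for adherence: 0.25 ± 1.96 × √(0.90 × 0.10/70 + 0.65 × 0.35/35) = 0.25 ± 0.1729, or .0771 to .4229. It reproduces, but does not concern validation of persistence and is not used below.

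**Inputs.** Fill and injection months are from Section 6.13, reading times from Sections 6.2.3 and 6.2.4, and the MPR and its cut from Section 7. Assumptions: 90 days per oral fill; each injection covers the interval to the next scheduled one (about 30 days after month 0, about 61 after month 1); month 3 is day 90; no oral bridging.

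**MPR read at month 3** = days recorded / 90.

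| Participant | Days recorded | MPR |
|---|---|---|
| Oral, one fill, never returns | 90 | 1.00 |
| Oral, still taking, refill not yet counted | 90 | 1.00 |
| Oral, still taking, month-3 refill counted | 180 | 2.00 |
| CAB-LA, month-0 injection only | 30 | 0.33 |
| CAB-LA, months 0 and 1, then stops | 30 + 61 = 91 | 1.01 |

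On these inputs the oral never-returner meets the 1.0 cut whether or not the month-3 refill is counted. Only the CAB-LA lapse at month 1 is visible.

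**Sensitivity to the assumptions.** For an oral participant with one fill, a 90-day supply gives 90/84 = 1.07 on day 84, 90/91 = 0.99 on day 91 and 90/92 = 0.98 on day 92. On day 90, an 84-day supply gives 84/90 = 0.93 and a 93-day supply 93/90 = 1.03. The value depends on pack size and reading day. Until a refill is collected it is the same for a stopper and a continuer.

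**MPR read over the whole study** (360 days or 12 months).
- Oral, never returns: 90/360 = 0.25.
- Oral, fills at months 0, 3 and 6 only: 270/360 = 0.75.
- CAB-LA, month 0 only: 1/12 = 0.08.
- CAB-LA, months 0, 1 and 3 only: (1 + 2 + 2)/12 = 0.42.

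The second and fourth participants collected their month-3 supply; the first and third did not. All four fall below 1.0, so the ratio cannot separate them on month-3 status.

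**The late reading.** An oral participant who collects fills to month 9 and then stops has 4 × 90/360 = 1.0 at month 12. A CAB-LA participant with injections to month 9 has (1 + 5 × 2)/11 = 1.0 at month 11. A stop after the last supply before the reading is therefore also hidden there, in both arms.

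**Section 6.6.1 at month 3.**
- Oral, stops on day 1: 3 months missed, which is not more than 3. Counted from the end of supply, the rule cannot be met until after month 6.
- CAB-LA, misses month 1: 3 − 1 = 2 months from the due date, or 3 from the month-0 dose. Neither is more than 3.
- Late readings: a stop after month 9 (oral, read at 12) or after month 8 (CAB-LA, read at 11) gives at most 3 months.

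**The case against.** The strongest reply is that self-report is the endpoint and records only support it. Section 6.2 has oral participants complete the persistence assessment every month, and the Appendix C item offers an answer for having stopped. This stands. A reader might infer that the endpoint cannot show an oral participant as stopped; the documents do not support that.

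A reader might also infer that CAB-LA participants must show a return dose to count as persistent. No text requires it. Section 6.2.3 asks for at least one injection and remaining on injections or oral bridging, and a CAB-LA stop after month 1 is hidden just as an oral stop is. The asymmetry is confined to lapses at the month-1 injection.

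Nor does the discontinuation rule make month-3 persistence complete by construction. No passage uses Section 6.6.1 to score persistence, and Section 6.6.2 ties it to three months of outreach. It cannot be met by month 3 in either arm, so it creates no contrast between them.

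It is tempting to turn the artefact into a percentage-point bias against CAB-LA. Any such figure merely returns the assumed rate of non-return, and it would describe the validation, not the primary comparison.

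Finally, the month-3 refill is itself a record, so claims extracted later can show whether it was collected. That is true, and it is the basis of the fix. The plan does not provide for it, however. Even with the refill counted, an MPR cut at 1.0 separates stoppers from continuers only if the supply happens to be shorter than the days elapsed.

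**Conclusion.** The concern holds as a weakness in the objective check of early persistence. Read at month 3, the MPR is about 1.0 for an oral initiator who never returns, against about 0.33 for a CAB-LA participant who misses the month-1 injection and about 1.01 for one who stops after it. Read over the whole study, it answers a different question in both arms. The month-3 values rest on about 90 days per oral fill, which the calendar implies but the documents do not state; other pack sizes or reading days move the value slightly around 1.0 without making it informative before the refill.

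The size of any effect on the reported comparison cannot be derived from the documents, and none is claimed.

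The gap around Section 6.6.1 does not depend on the supply assumption. The rule cannot register a stop by month 3, nor one in the last three months before the late reading, and its relation to Sections 6.2.3, 6.2.4 and 7 is not stated.

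**What to change.** Keep self-report as the measure. In both arms, validate persistence at month 3 and at end of study by whether the fill or injection due at that time point (month 3, then month 12 for oral and month 11 for CAB-LA) was obtained within 30 days, the window Section 6.14.1.2 already uses for retention. Count documented oral bridging as persistent in the CAB-LA arm, as Section 6.2.3 does. State the days' supply per fill and the date to which records are read. If MPR is kept, present it as a whole-study summary of supply.

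Reconcile Section 6.6.1 with Sections 6.2.3, 6.2.4 and 7, and state whether it plays any part in scoring persistence.

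The cost is wording in those sections and reading pharmacy and EHR records 30 days further, with no new visits or surveys. There are two downsides. Validated persistence is final one month later. The check also overlaps with retention-in-care and moves somewhat toward timeliness, although persistence is defined as independent of adherence; a participant who obtains the due supply after day 30 would fail validation while still on PrEP. Reporting self-report and the record check side by side keeps that visible.

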6.2.5. Adherence

6.2.5.1. Definition: Taking PrEP in line with medical advice/using PrEP appropriately (critical for efficacy) .

6.2.6. Adherence Assessment CAB-LA

6.2.6.1. Adherence to the dosing schedule will be assessed at month 3 (early adherence) and end of study by:

A) Estimating the number of individuals who missed one or more consecutive injections without taking daily oral bridging PrEP while not on CAB-LA injections and mean and median number of injections missed during a 6- and a 12-month period.

6.2.7. B) Estimating the number of individuals who received the injections seven or more days later than their scheduled injection visit and the mean and median duration of delayed injections. Adherence Assessment Oral PrEP

6.2.7.1. Adherence to the dosing schedule will be assessed at months 3 (early adherence) and 12 by:

A) Estimating the number of individuals who reported three or more days of oral PrEP missed and the mean and median number of days they missed.

B) Estimating the number of individuals who had a gap of >90 days between the end of the days of supply of a dispensing and the start date of the next fill.

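### Adherence item B registers only participants who come back, in both arms, so permanent stopping lowers the event percentage and can bias the comparison in either direction

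*Combined protocol and SAP*

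**What the plan says.** Sections 6.2.6-6.2.7 give two adherence items per arm.

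- CAB-LA item A covers missed injections: "Estimating the number of individuals who missed one or more consecutive injections without taking daily oral bridging PrEP while not on CAB-LA injections".
- CAB-LA item B covers lateness: "individuals who received the injections seven or more days later than their scheduled injection visit and the mean and median duration of delayed injections".
- Oral item B is a "gap of >90 days between the end of the days of supply of a dispensing and the start date of the next fill".

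In the paragraph of Section 7 on the co-primary adherence endpoint, item B becomes "The percent of CAB-LA participants who received any injections seven or more days later than their scheduled injection", to be compared with the oral percentage having the 90-day gap. No rule covers an injection never given or a prescription never refilled, and the denominator is not limited to those still on treatment.

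Section 6.6.1 defines discontinuation ("Participants will be deemed as having discontinued PrEP if they miss more than 3 consecutive months for PrEP") but does not link it to adherence. The only exclusion from the final analysis on treatment grounds is a regimen switch before six months (Section 6.5.1).

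**The concern.** An event that requires receipt cannot happen to someone who never returns. In a two-by-two table, a participant who stops with no earlier late injection can only fall in the not-late cell. Early stoppers also have fewer injections at risk: one who stops after month 1 has one follow-up injection that could be late, and a completer has six. The longest delays, those that never end, drop out of the mean and median.

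The oral item has the same structure, because a gap that is never closed by a new fill has no end date. On this item worse behaviour therefore lowers the event percentage in either arm. At stake is whether one part of a co-primary comparison can be interpreted when the arms stop at different rates, and a difference in stopping is what the study expects.

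**Working it through.** **The plan's own figure.** Section 7 assumes .90 of 70 and .65 of 35. The interval is 0.25 ± 1.96 × √(.90×.10/70 + .65×.35/35) = 0.25 ± 0.1729, or .0771 to .4229, as stated. It does not depend on item B. The .90 is an adherence assumption and is not used below as one minus a stopping rate.

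**Inputs from the documents.** Six follow-up injections, at months 1, 3, 5, 7, 9 and 11 (Section 6.13.1); 70 and 35 participants (Section 5.3).

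**Assumptions, because the documents give no rates.**
- Each injection given has an independent probability q = 5% of being seven or more days late.
- A share s stops for good, with constant hazard h = 1 − (1−s)^(1/6) per scheduled injection.
- 5% of oral continuers have a gap of more than 90 days and then refill.

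**CAB-LA item B.** Completers never late: (1−s) × 0.95^6 = (1−s) × 0.735. Stoppers never late: N = Σ (1−h)^k × h × 0.95^k, for k = 0 to 5.
- As written: 1 − (1−s)×0.735 − N.
- Never-given injections counted: 1 − (1−s)×0.735.

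For s = 10%: h = 0.0174 and N = 0.0885. As written, 1 − 0.6616 − 0.0885 = 25.0%; counted, 33.8%.

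For s = 30%: h = 0.0577 and N = 0.2673. As written, 1 − 0.5146 − 0.2673 = 21.8%; counted, 48.5%.

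| Stopping | As written (of 70) | Never-given counted (of 70) |
|---|---|---|
| 0% | 26.5% (18.5) | 26.5% (18.5) |
| 10% | 25.0% (17.5) | 33.8% (23.7) |
| 20% | 23.4% (16.4) | 41.2% (28.8) |
| 30% | 21.8% (15.3) | 48.5% (34.0) |
| 50% | 18.3% (12.8) | 63.2% (44.3) |

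At 30% stopping, q = 2% gives 9.4% against 38.0%, and q = 10% gives 38.9% against 62.8%.

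The stopping pattern matters little. If the first injection missed for good is uniform over the six, stoppers are ever late in 11.7% (the mean of 1 − 0.95^k for k = 0 to 5). At 30% stopping the figure as written is then 0.7 × 26.5% + 0.3 × 11.7% = 22.1%.

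**Between arms.** Oral as written: (1−s) × 5%. Oral with non-returners counted: s + (1−s) × 5%. Differences are CAB-LA minus oral, in points, from unrounded values.

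| Stopping, CAB-LA / oral | As written | Counted in both arms |
|---|---|---|
| 10% / 35% | 25.0 − 3.25 = +21.7 | 33.8 − 38.25 = −4.4 |
| 30% / 30% | 21.8 − 3.5 = +18.3 | 48.5 − 33.5 = +15.0 |
| 35% / 10% | 21.0 − 4.5 = +16.5 | 52.2 − 14.5 = +37.7 |

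Higher is worse. In the first row the wording hurts CAB-LA; in the last it flatters CAB-LA. The counted oral figures are upper ends, because an oral participant who stops within 90 days of the end of follow-up could not yet meet the limit.

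**Correcting CAB-LA alone**, at 10% / 35%: 33.84 − 3.25 = +30.6, further from −4.4 than the present +21.7.

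**The case against.** The plan separates missed from late injections. Item A counts the never-returner who takes no oral bridging. Persistence counts those "who remained on injectable PrEP or oral bridging at months 3 and 11", so stoppers fail there. A duration of delay naturally describes injections that were given. Most of the gap between the two CAB-LA columns is the assumed stopping rate handed back. As written, tripling stopping from 10% to 30% moves item B by about 3 points, or 2 of 70 people. If stoppers tend to be late first, their earlier late injection still counts and the effect shrinks. At month 3 only two follow-up injections are at risk.

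These points limit the size but do not supply the missing rule. Nothing combines item A or persistence with item B, and item B is compared between arms by itself. Item A is also weaker protection than it looks: Section 7 describes it as "compare the percent of CAB-LA participants who reported missing one or more injections during the study period", yet the CAB-LA persistence questionnaire in Appendix B has no question on missed injections.

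A reader might infer that the wording tilts the co-primary comparison towards CAB-LA. The documents do not support that. Oral item B misses permanent stoppers in the same way. The background (Section 2.1.1) describes short oral persistence and the hypothesis (Section 2.3.1) expects better CAB-LA persistence; if both hold, the wording works against CAB-LA.

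**Conclusion.** The point holds for both arms. Item B cannot register a participant who leaves for good without an earlier event, and that participant lowers the arm's percentage. No section says such a person is scored as on time; this follows from a denominator of all participants in the arm.

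Under a 5% late risk and 10% to 30% stopping, CAB-LA item B reads about 25% falling to 22%, against 34% rising to 49% if never-given injections count. The between-arm difference can move by more than 20 points in either direction when stopping differs strongly (35% against 10%), and by about 3 points when both arms stop at 30%. These sizes rest on assumed rates and on lateness being independent of stopping. That stopping lowers the percentage within an arm rests only on the wording; the net direction between arms cannot be stated in advance. The plan should be changed here, although item A and persistence give partial protection and the stated interval is unaffected.

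**What to change.** Amend Sections 6.2.6-6.2.7 and Section 7 for both arms together.

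1. **CAB-LA event:** a scheduled injection not received within the plan's existing seven-day limit, whether given later or never, over all injections scheduled up to the time point. State how oral bridging counts, consistently with item A and the persistence definition, and how participants who switch after six months are handled.
2. **Oral event:** more than 90 days after the end of supply without a new fill, whether or not a later fill occurs, counted to the end of follow-up. State how a lapse still under 90 days at that point is treated.
3. **Delay:** report the mean and median among injections given, with never-given injections as a separate category or as censored.

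The cost is a few sentences. The injection and dispensing dates are already needed for item B. Item B percentages will look less favourable in both arms and will overlap more with item A and persistence, which the report should acknowledge.

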6.2. Description of Study Procedures

Before any screening procedure is performed, informed consent will be obtained. Labs will be taken at baseline and months 3, 5, 7, 9, and 11 for the CAB-LA cohort and at baseline and months 3, 6, 9, and 12 for the Oral PrEP cohort (only collected through standard of care). Participants will complete a baseline evaluation and be introduced to a support group at baseline. Patients will complete assessments within the TheraPay App. Clinicians will complete assessments outside of the app. Patients in both cohorts will complete baseline demographic surveys in month 0, patient reported outcomes (PRO) data collection set 1 in months 1, 5, and 11 and PRO data collection set 2 in months 3, 9, and 12. Patients in the CAB-LA PrEP cohort will complete persistence assessments in months 1, 3, 5, 7, 9, and 11. Patients in the Oral PrEP cohort will complete persistence assessments every month from months 1 through 12. Clinic staff will complete surveys at baseline, month 6, month 12, and at the end of the study. The

schedule of assessments for the CAB-LA PrEP cohort, Oral PrEP cohort, and clinicians is presented in figure 6a. Instruments are in Appendix B for the CAB-LA cohort, in Appendix C for the Oral PrEP cohort, and Appendix D for clinicians. Patient incentives for completing the assessment activities are outlined in Appendix E.

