You are treated with less respect than other people are. 
  Never  Less than once a year  A few times a year  A few times a month  At least once a week  Almost every day 	15
People act as if they're better than you. 
  Never  Less than once a year  A few times a year  A few times a month  At least once a week  Almost every day 	16
What do you think is the main reason for these experiences? (Select 1) 
  Your gender  Your sexual orientation  Your race  Your religion  Some aspect of your physical appearance  Your education or income level  Other: [Write in] 	17

End Message: Thank you for completing this survey!

Persistence Assessment

Activity Title: Are You Still Taking PrEP?

Activity Description: In this short survey, we'll ask you some questions about your PrEP journey and any challenges you may have encountered.

Activity:

1. Are you still taking PrEP medicine by mouth?

- Yes, I am taking PrEP (branching logic to question 4)
- No, I stopped taking PrEP (branching logic to questions 2)

2. Over the past week, how many days did you miss taking PrEP?

- 0
- 1
- 2
- 3
- 4
- 5
- 6

7

3. If you stopped taking PrEP, which of the following best describes the reason(s) why? [Select up to 2]

- I no longer feel I needed to take PrEP (branching logic to question 3 if selected)
- It was too difficult to take PrEP with my schedule
- I did not want people to know I was taking it or I felt I was being judged by others for taking PrEP
- I did not like the side effects
- I take too many medications
- There were too many appointments as part of my PrEP care
- I tested positive for HIV
- Other: [Fill in the blank]

4. Which of the following best describes why you no longer feel you need to take PrEP?

- I am no longer having sex
- I am in a monogamous relationship
- I am no longer using injectable drugs
- My partners and I are all regularly using condoms and getting tested for HIV
- Other: [Fill in the blank]

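### The oral side of the co-primary adherence comparison has no look-back period or aggregation rule, while CAB-LA is scored on any missed injection over the study period

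*Combined protocol and SAP*

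**What the plan says.** Adherence is a co-primary endpoint, and the sample-size statement rests on it.

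- **Section 6.2.7.1, item A (oral):** counts "individuals who reported three or more days of oral PrEP missed". Assessment times are months 3 and 12. No counting period is given.
- **Section 7 (the test):** sets the arms against each other, taking on the CAB-LA side those "who reported missing one or more injections during the study period to the percent of oral PrEP participants who reported three or more missed days". The study period is attached to the CAB-LA side only.
- **Appendix C, Persistence Assessment, question 2:** "Over the past week, how many days did you miss taking PrEP", answered 0 to 7. This is the only item that yields oral missed days.
- **Section 6.2:** "Patients in the Oral PrEP cohort will complete persistence assessments every month from months 1 through 12".
- **Study Outcomes Table and Appendix G:** place adherence and persistence at month 3 and end of study.
- **Section 7, Sample Size:** the planning inputs read "Assuming adherence proportions of .90 and .65 and sample sizes of 70 and 35 in the CAB-LA and oral PrEP arms respectively". From these it derives a 95% interval of .0771 to .4229 for the arm difference.

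No section says whether one survey, any survey or some combination of surveys decides an oral participant's status.

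**The concern.** Two analysts following this plan could score the same oral participants differently and report different co-primary results, and the choice could be made after the data are seen.

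The reading that the timing language most supports is also lopsided. If only the month-3 and month-12 surveys count, an oral participant can fail only on misses in two particular weeks. A CAB-LA participant can fail at any scheduled injection. The oral arm then has far less opportunity to be classed non-adherent, for a reason unrelated to behaviour.

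The planning value of .65 for oral adherence has no defined meaning either, because the proportion it refers to depends on the missing rule.

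**Working it through.** **1. The plan's own figure.** Inputs from Section 7: .90 and .65, n = 70 and 35.

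SE = sqrt(.90 × .10/70 + .65 × .35/35) = sqrt(.001286 + .006500) = .0882. Half-width = 1.96 × .0882 = .173. Interval = .25 ± .173 = .0771 to .4229. This reproduces the stated interval.

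**2. Exposure on each reading.** Months 3 and 12 only: 2 × 7 = 14 days, and 14/365 = 4%. All 12 monthly surveys: 12 × 7 = 84 days, and 84/365 = 23%. For CAB-LA, every scheduled injection counts.

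**3. Effect of the reading.** The documents give no daily miss rate, so q is an assumption. Days are first taken as independent with q common to all. The chance of three or more missed days in one surveyed week is

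P7 = 1 − [(1−q)^7 + 7q(1−q)^6 + 21q²(1−q)^5].

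Failing at either of two surveys has probability 1 − (1−P7)^2. Failing at any of 12 has probability 1 − (1−P7)^12. The difference is .90 minus oral adherence.

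| Assumed q | P7 | Non-adherent, month 3 or 12 | Difference | Non-adherent, any of 12 | Difference |
|---|---|---|---|---|---|
| 5% | .0038 | 0.8% | .90 − .992 = −9 points | 4.4% | .90 − .956 = −6 points |
| 10% | .0257 | 5.1% | .90 − .949 = −5 points | 26.8% | .90 − .732 = +17 points |

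If q varies between people (beta, mean 5%, first shape parameter 0.5), non-adherence is 3.9% or 12.7%. The differences are .90 − .961 = −6 and .90 − .873 = +3 points.

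**4. What .65 implies.** For 35% oral non-adherence, q must be about 23% on the month-3-or-12 reading and about 11% on the any-of-12 reading.

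**5. Can the data be collected as printed?** In Appendix C, question 1 sends those still taking oral PrEP to question 4, past the missed-days item at question 2. Only those who have stopped reach it. In the CAB-LA form (Appendix B) question 4 is the challenges item for continuing users. In the oral form that item is question 5, so the routing appears not to have been renumbered. The CAB-LA form has no question on missed injections, although Section 7 treats them as reported.

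**6. CAB-LA definition.** Section 6.2.6.1 counts missed injections only where daily oral bridging was not taken. Section 7 carries no such exception.

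**The case against.** The strongest reply is that the plan is less open than it looks. Section 6.2.7.1, the Study Outcomes Table and Appendix G all point to month 3 and end of study. With a past-week item, the natural reading is the report given at those two surveys. That stands as the best-supported reading of timing. It does not answer the concern, because it is the reading that sets 14 surveyed days against the whole injection schedule, and Section 7 does not state it.

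It is also fair that every miss rate here is assumed. At a common 5% rate the two readings differ by about 4 points with no change of sign, well inside the 17-point half-width. Reversal needs a higher rate or variation between people.

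Three stronger inferences are not supported:

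- **Three conflicting oral windows.** Sections 6.2.7.1 and 7 state none and only the form states one. The fault is omission.
- **Adding missed days over all 12 surveys.** Three or more of 84 days would class 79.7% of oral participants non-adherent at q = 5% and 99.2% at 10%, or differences of +70 and +89 points. No section tells anyone to add reports across surveys, so these figures should not be used to size the problem.
- **A rival CAB-LA test window.** Section 6.2.6.1 mentions the "mean and median number of injections missed during a 6- and a 12-month period". This reads as a descriptive summary, not a second period for the tested proportion.

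**Conclusion.** The concern holds as an unstated oral look-back and aggregation rule in a co-primary comparison whose other arm is scored over the study period. The literal two-survey reading gives the arms unequal opportunity to fail. Moving from that reading to any of 12 surveys shifts the arm difference by about 22 points at an assumed 10% miss rate (from −5 to +17), and by about 4 points at 5% (from −9 to −6). These sizes rest on assumed miss rates, independent days, all surveys answered and CAB-LA adherence at the plan's .90.

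The absence of a rule, and the routing that keeps continuing oral users from the missed-days item, rest on no assumption. The sample-size interval is arithmetically right, but its .65 refers to a proportion that the plan has not defined.

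**What to change.** State one rule, in the same words, in 6.2.7.1 and Section 7, with the same accumulation period in both arms. For example:

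- **Oral:** non-adherent by time T if three or more missed past-week days are reported at any monthly survey up to T.
- **CAB-LA:** non-adherent by T if any injection scheduled up to T is missed.
- **Times:** test at month 3 and at end of follow-up.

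In addition:

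- State how unanswered surveys are handled, and add a sensitivity analysis using only the month-3 and end-of-study surveys.
- Reconcile the oral-bridging exception in 6.2.6.1 with its absence from Section 7.
- Correct the Appendix C routing so that participants still taking oral PrEP answer the missed-days item.
- Name the data source for missed injections.

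**Cost.** The form's routing must be edited, so this is more than wording in 6.2.6, 6.2.7 and Section 7. Oral failure will be higher than on the two-survey reading, by up to about 22 points at a 10% miss rate (26.8 − 5.1 = 21.7). That favours CAB-LA, and the documents do not dictate the choice, so it should be fixed before data are seen. The any-survey rule also depends on completion: at 10%, six answered surveys give 1 − .9743^6 = 14.5% non-adherent against 26.8% with twelve, so non-responders look more adherent. Oral misses would still be sampled in only 12 of 52 weeks, and the report should say so.
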